- Have more or equal than grade 3 adverse events
- 135 Have conditions that are not suitable for continuation of study
- 136 Protocol violations that significantly affect data collection or interpretation
- 137 Pregnancy
- 138 Need to increase the dose of iron chelation while currently in study
- 139 Have indication for proton pump inhibitor or resveratrol such as gastrointestinal bleeding
- 140 Withdrawal of informed consent
- 141
- 142 Sample Size Calculation
- Expected standardized difference of 0.22 from the Eghbali et al. [22] study which found that adjunct pantoprazole with iron chelators could lower serum ferritin more than iron chelators alone by decreasing serum ferritin from 1444 ± 613 ng/mL to 1197 ± 956 ng/mL and 1928 ± 694 ng/mL to 1501 ± 385 ng/mL respectively. If alpha = 0.05 and beta = 0.2, the estimated sample size is 20 persons in each study group [31] as shown in Table 1.
- **Table 1** Estimated stepped rules of thumb for required trial sample size/treatment arm [31].

Standard difference	80% powered main trial	90% powered main trial
Extra small ($\delta < 0.1$)	50	75
Small $(0.1 \le \delta < 0.3)$	20	25
Medium $(0.3 \le \delta < 0.7)$	10	15
Large ($\delta \ge 0.7$)	10	10

149

150 Study Intervention

- Divide the patients into three study groups in a 1:1:1 ratio using stratified randomization
 based on gender (male and female) and serum ferritin (<1,000, equal to 1,000 or >1,000
 ng/mL). The randomization will be used web-based randomization.
- Allocation concealment will use sealed envelopes to ensure concealment, A staff member not involved in this study will place the study drugs into opaque, sealed envelopes and label them into unique codes. The patients will receive the study drug corresponding to the code on their envelope, without knowing the content. The code lists will be securely stored and remain inaccessible to the research team during the trial.
- This study will use a double-blind technique for patients and outcome assessors. Three study compounds including omeprazole, resveratrol and placebo will be prepared and filled in gelatin capsules with the same appearance as follows; 20 mg omeprazole capsule, 250 mg resveratrol capsule and 20 mg maltodextrin. The capsules will be packed in a white plastic bottle (30 capsules each) and labeled codes under the bottles.
- The patients in Group 1 will take an omeprazole capsule orally twice daily (total 40 mg/day) in the morning and evening before meal for 6 months.

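### The ferritin figures behind the planning effect contradict the sentence they support, and the standardised difference of 0.22 is given without a derivation

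*Protocol*

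**What the plan says.** The Sample Size Calculation in the protocol opens with an "Expected standardized difference of 0.22", attributed to reference 22. It reports the finding of that study as "adjunct pantoprazole with iron chelators could lower serum ferritin more than iron chelators alone". The supporting figures are two before-and-after pairs: "from 1444 ± 613 ng/mL to 1197 ± 956 ng/mL and 1928 ± 694 ng/mL to 1501 ± 385 ng/mL respectively". The text then sets the error rates ("If alpha = 0.05 and beta = 0.2") and concludes that "the estimated sample size is 20 persons in each study group [31] as shown in Table 1". Table 1 is a stepped rule of thumb. At 80% power, its Small row (0.1 up to but not including 0.3) gives 20 per arm and its Medium row (0.3 up to but not including 0.7) gives 10.

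No formula, SD or correlation is given for the step from the four means and SDs to 0.22.

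**The concern.** The sentence names the adjunct arm first and chelators alone second, and closes the two pairs with *respectively*. On that reading the arm said to have done better had the smaller fall, in absolute and in relative terms. This study is the only quantitative basis the protocol gives for the expected effect on serum ferritin, its primary outcome. The trial's hypothesis is that an active adjunct lowers ferritin compared with placebo.

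Two things are at stake. The evidence quoted for the direction of effect does not show that direction as printed. And a reader cannot tell which contrast or which SD the 0.22 stands for, so the row chosen in Table 1 cannot be checked.

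**Working it through.** **Inputs** (all from the protocol, Sample Size Calculation):

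| Arm, in the stated order | Before: mean (SD) | After: mean (SD) | Fall |
|---|---|---|---|
| Pantoprazole + chelators | 1444 (613) | 1197 (956) | 247 (247/1444 = 17.1%) |
| Chelators alone | 1928 (694) | 1501 (385) | 427 (427/1928 = 22.1%) |

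**Direction.**
- Difference in falls: 427 − 247 = 180 ng/mL, in favour of chelators alone.
- Baseline gap: 1928 − 1444 = 484. Final gap: 1501 − 1197 = 304. The adjunct arm ends lower, but its head start shrank by 180.
- If the two pairs were transposed, the adjunct arm would fall 427 against 247 but end higher (1501 against 1197).

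So on either reading, change from baseline and final value point in opposite directions.

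**Trying to reproduce 0.22.** Arm sizes in the cited study are not given, so the SDs are pooled with equal weights.
- Baseline SDs: √((613² + 694²)/2) = 655; 180/655 = 0.27.
- Follow-up SDs: √((956² + 385²)/2) = 729; 180/729 = 0.25.
- Final values: 304/729 = 0.42.
- SD of change: in each arm √(s₀² + s₁² − 2·r·s₀·s₁), then pooled over arms. The correlation r is not in the protocol, so it is assumed over a range:

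| Assumed r | Pooled SD of change | 180/SD |
|---|---|---|
| 0 | 980 | 0.18 |
| 0.34 | 818 | 0.22 |
| 0.5 | 730 | 0.25 |
| 0.7 | 602 | 0.299 |
| 0.8 | 527 | 0.34 |
| 0.9 | 438 | 0.41 |

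The planned 0.22 appears as a between-arm difference in change only near r = 0.34. As the figures are printed, it then favours chelators alone. Transposing the pairs reverses the sign of every entry and leaves its size unchanged.

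**Effect on the protocol's own lookup.** The values 0.25, 0.27 and the change-SD results up to r = 0.7 fall in the Small row (20 per arm). The final-value result of 0.42 and the change-SD results at r = 0.8 and 0.9 fall in the Medium row (10 per arm).

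**What 20 per arm can detect.** For a two-arm t-test at two-sided 5% and 80% power, the detectable difference is about 0.91 SD. The normal approximation gives (1.96 + 0.84) × √(2/20) = 0.89.

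**The case against.** The strongest reply is that this may be a slip of reporting with little consequence. The pairs may simply have been transposed, and then the adjunct arm has the larger fall. The size of the difference, 180 ng/mL, is the same either way. Most ways of scaling it stay in the Small row of Table 1, so correcting the paragraph might well leave 20 per arm where it is under that rule. Even as printed, the adjunct arm has the lower final mean. All of this stands, and it limits the point to an inconsistency and a missing derivation. It does not remove the inconsistency: the lower final mean comes with a baseline 484 ng/mL lower, and the transposed reading has the adjunct arm finishing higher.

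A reader might also infer more than the protocol supports.

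- *That 0.22 was scaled by an unsuitable SD.* Dividing 180 by 803, the pooled before-and-after SD of the first-listed arm alone, gives 0.224. But 427/1928 = 0.2215, 247/√(613² + 956²) = 0.2175 and the between-arm SD of change at r of about 0.34 (0.220) are all closer to 0.22. The last is a legitimate between-arm scale. Which route was taken is unknown.
- *That regression to the mean explains the 180 ng/mL.* For that alone to shrink a gap of 484 to 304, the slope of follow-up on baseline would have to be about 304/484 = 0.63. The protocol gives no slope or correlation.
- *That the contradiction is what makes 20 per arm too few.* At 0.22, a standard two-sided calculation needs about 325 per arm for 80% power. That gap comes from reading the size off a rule-of-thumb table, and it exists whichever arm had which values.

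**Conclusion.** The point holds as an internal contradiction with an untraceable planning figure. As printed, the comparator's ferritin fell 180 ng/mL more than the adjunct arm's (427 against 247; 22.1% against 17.1%), while the sentence claims the reverse. The standardised difference of 0.22 cannot be reproduced from the stated figures without a correlation that the protocol does not give. Reasonable alternatives run from 0.18 to 0.42 and span two rows of Table 1, so the size depends on an unstated choice even under the protocol's own rule.

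The direction result rests only on reading the two pairs in the order in which the arms are named. The standardised values also assume equal weighting of the arms and, for the change-based ones, r between 0 and 0.9. The protocol does not show that the cited study contradicts the trial's hypothesis. It shows only that the figures and the conclusion, as transcribed, cannot both be right about the fall in ferritin.

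**What to change.** Check the cited pantoprazole study and correct either the assignment of values to arms or the stated direction. Then show in one line how the standardised difference is obtained: which contrast (change or final value), which between-arm SD, and any correlation assumed.

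If the source does not support an effect in favour of the adjunct, drop it as the basis. In place of the 0.22 claim, state what 20 per arm can detect: about 0.91 SD at 80% power, two-sided 5%, two-arm t-test.

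The cost is one rewritten paragraph and, in the second case, a less favourable figure in print. Conduct of the trial is not affected.

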- 192 2) Hb typing will be performed at the Hematology laboratory, Department of Internal Medicine,193 Chiang Mai University.
- 3) Serum BUN, Cr, electrolytes, AST, ALT, ALP, sFt, SI and TIBC will be quantified using an
 automated Roche Cobus Biochemical Analyzer machine according to the manufacturer's
 instruction at the Central Laboratory, Maharaj Nakorn Chiang Mai Hospital, Faculty of
 Medicine, Chiang Mai University.
- 4) Serum iron parameters will be quantified at the Oxidative Stress Laboratory, Department of
 Biochemistry, Faculty of Medicine, Chiang Mai University using specific reagents and
 techniques as described below.
- 4.1) LPI using rhodamine B fluorescence probe [32]
- 4.2) NTBI using NTA chelation/iron chelator fluorescence beads/flow cytometry [32]
- 4.3) Hcd using a sandwich ELISA kit (ABBEXA limited company, Cambridge, UK)
 according to the manufacturer's instruction [33]
- 4.4) ERFE using a sandwich ELISA kit (ABBEXA limited company, Cambridge, UK)
 according to the manufacturer's instruction [34]

208 Statistical Analysis

207

All patients who receive at least 1-time study drug will be analyzed in an Intention-to-treat 209 210 analysis. Patients who receive at least 80% of the study drug will be analyzed in a Per-protocol analysis. Descriptive statistics will be used for the analysis of demographic data. Primary outcome 211 and secondary outcomes [continuous variable] will be analyzed using Friedman's analysis of 212 variance (ANOVA) test. Secondary outcomes [dichotomous variable] will be analyzed using Chi-213 square or Fisher exact test for independent data or Cochran's Q test for dependent data. The 214 association between continuous variables will be analyzed using Pearson's or Spearman's test. 215 216 Accordingly, a P-value <0.05 is considered statistical significance.

217 Duration of Study Plan

```
219
```

References 220

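### The one test named for continuous outcomes cannot adjust a comparison of arms for baseline ferritin or the stratification factors

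*Protocol*

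**What the plan says.** Study Intervention (Protocol): "Divide the patients into three study groups in a 1:1:1 ratio using stratified randomization", with strata "based on gender (male and female) and serum ferritin (<1,000, equal to 1,000 or >1,000" ng/mL). Ferritin must therefore be known before allocation.

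Research Design (Protocol): blood is drawn at the first visit, month 3 and month 6, and ferritin is in the panel each time.

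Statistical Analysis (Protocol): the primary outcome and "secondary outcomes [continuous variable] will be analyzed using Friedman's analysis of" variance. The blocks of that test are not defined. No covariate, stratum term or adjusted model is named.

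Primary Objective (Protocol): ferritin reduction on either adjunct is to be judged against placebo.

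Sample Size Calculation (Protocol): "If alpha = 0.05 and beta = 0.2, the estimated sample size is 20 persons in each study group", for a standardised difference of 0.22.

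**The concern.** The design spends effort on balancing the arms by sex and ferritin, and it collects a pre-treatment value of the primary outcome. The analysis has no way to use either when it compares arms. Eligible ferritin runs from 300 ng/mL upwards with no ceiling, so patients can start far apart, and the open-ended upper stratum still leaves room for chance imbalance with 20 per arm. If baseline predicts month-6 ferritin, a between-arm comparison without it has a larger error variance and carries that imbalance into the estimate. If the stratification factors are prognostic, leaving them out gives standard errors that are too large for the design used.

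This is more than detail left to a statistical analysis plan. The protocol names a specific test with no place for covariates, so a later plan could adjust only by departing from it.

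**Working it through.** **1. What Friedman's test can use.** It ranks values within blocks and compares the repeated conditions. With the patient as block and the three visits as conditions, baseline ferritin is the first condition, and stable differences between patients drop out. But the conditions compared are visits, not arms. Sex, stratum and baseline cannot enter as covariates, and no contrast with placebo results. Simulation with 20 per arm, all arms pooled over three visits and 2,000 runs per setting shows the consequence:

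- Common fall of 0.5 SD, no difference between arms: the test was significant in 82% (correlation 0.5) to 99.8% (0.8) of runs.
- Effect of 0.22 SD in one arm only: it was significant in 6.5% to about 9% of runs.

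**2. The protocol's own figure.** The 20 per arm is the entry for a small effect at 80% power in Table 1 ("Estimated stepped rules of thumb for required trial sample size/treatment arm"). The usual two-group formula, two-sided 0.05 (sidedness is not stated), gives 2(1.96 + 0.842)²/0.22² = 324.3, so 325 per arm. With 20 per arm, power is Φ(0.22/√(2/20) − 1.96) = Φ(0.696 − 1.96) = 10.3%.

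**3. Gain from baseline adjustment.** Let r be the correlation between baseline and month-6 ferritin. The protocol does not give it, so 0.5 to 0.9 is an assumed range. Relative to month-6 values alone, the error variance is

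- baseline-adjusted (ANCOVA): f = 1 − r²
- change score, equal SDs at both times: f = 2(1 − r)
- ANCOVA over change score: (1 − r²)/(2(1 − r)) = (1 + r)/2

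Taking 0.22 as a multiple of the month-6 SD, power at 20 per arm is Φ(0.22/√(f × 2/20) − 1.96), and n per arm for 80% power is 324.3 × f, rounded up.

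| r | ANCOVA vs month-6 only | Change vs month-6 only | ANCOVA vs change | Power, ANCOVA | Power, change | n per arm, ANCOVA |
|---|---|---|---|---|---|---|
| 0.5 | 0.75 | 1.00 | 0.75 | 12.4% | 10.3% | 244 |
| 0.7 | 0.51 | 0.60 | 0.85 | 16.2% | 14.4% | 166 |
| 0.8 | 0.36 | 0.40 | 0.90 | 21.2% | 19.5% | 117 |
| 0.9 | 0.19 | 0.20 | 0.95 | 35.8% | 34.3% | 62 |

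Reaching 80% power with 20 per arm would need r of about 0.97.

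**4. How far the equal-SD assumption matters.** The factor 1 − r² does not need it; the change-score columns do. The only SDs in the protocol come from the source study: 613 to 956 in the first group listed and 694 to 385 in the second. At r = 0.8:

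- First group: ANCOVA 956² × 0.36 = 329,017; change 613² + 956² − 2 × 0.8 × 613 × 956 = 352,060; ratio 0.93.
- Second group: ANCOVA 385² × 0.36 = 53,361; change 694² + 385² − 2 × 0.8 × 694 × 385 = 202,357; ratio 0.26.

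So the 0.90 in the table is a reference value, not a forecast.

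**5. Cost.** Log baseline, sex and a two-level stratum take three degrees of freedom: with 60 patients in three arms, the residual falls from 57 to 54.

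**The case against.** A reader might infer that the plan ignores baseline ferritin altogether. It does not: with patients as blocks, the natural reading, baseline is used as the first repeated measure and spread in starting level does not inflate the error of that test. What stands is narrower: baseline cannot adjust a comparison of arms.

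A reader might also put the loss as a fall in detectable difference from 0.91 to 0.55 SD (t-based, 80% power, r = 0.8; 0.909 × √0.36 = 0.545). That measures the loss against a month-6-only comparison, which the protocol nowhere specifies. Against change scores with equal SDs the fall is only from 0.909 × √0.40 = 0.575 to 0.545.

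Nor do the documents show that most month-6 variation is starting level. No correlation is given, and at r = 0.5 baseline explains only 25%. Nothing shows that sex predicts ferritin response, and the ferritin stratum adds little once log baseline is in the model. Stratification already limits some imbalance.

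The strongest objection is that the larger fault is the absence of any between-arm comparison, and that covariates are a detail of whatever model replaces the test. The first half is right. But an unadjusted three-group test at month 6 would mend that fault and still discard baseline, so adjustment should be written in at the same time.

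**Conclusion.** The point holds in a limited form. The only stated method for continuous outcomes cannot adjust a comparison of arms for baseline ferritin, sex or ferritin stratum, although all three are collected and two define the randomisation strata. For assumed correlations of 0.5 to 0.9, adjustment would leave 75% to 19% of the variance of a month-6-only comparison. With equal SDs at the two times, it would leave 75% to 95% of the variance of a change-score comparison. The direction is secure; the size rests on a correlation that the documents do not supply.

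The gain should not be read as rescuing the sample size. At the planned difference of 0.22, power with 20 per arm goes from 10.3% to 21.2% at r = 0.8 and 35.8% at r = 0.9. This is a cheap and worthwhile improvement in precision, second in importance to having a comparison with placebo at all.

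**What to change.** Replace Friedman's test as the main analysis of continuous outcomes, before unblinding:

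- **Ferritin:** regress log month-6 ferritin on arm, log baseline ferritin, sex and ferritin stratum (below 1,000 vs 1,000 or above). Report each active-versus-placebo contrast as a ratio of geometric means with a 95% confidence interval. A repeated-measures version with the same terms would also use month 3.
- **Other continuous biomarkers:** use the same model, each with its own baseline value. Take logs only where values are strictly positive. LPI and NTBI may be zero or undetectable; use the raw or a rank scale there.
- **Strata:** the separate level at exactly 1,000 ng/mL will be almost empty. Reword the Study Intervention text so that it and the model use the same two levels. Check the boundary against Inclusion Criteria, where the lower ferritin range includes 1,000.

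The cost is a revision of the analysis and stratification wording and about three degrees of freedom; no new data are needed. The sample size needs separate attention.

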
- 3. To study the association between resveratrol and changes in HbF levels
- 84 85
- 4. To assess the adverse effects of adjunct omeprazole or resveratrol with iron chelators
- 86

87 Ethics

88 This study has been approved by the Human Experimentation Committee Research Institute for Health Sciences and authorized by Associate [name], Ph.D., a 89 90 Chairman of the Committee, Faculty of Medicine, Chiang Mai University, Chiang Mai 50200, Thailand, Certificate Number: 476/2024 (English version) and 476/2567 (Thai version), Date: 17th 91 92 December 2024. Adherence to ethical guidelines was of prime importance throughout the study process. All patients will be fully informed about the particulars of the study and willingly provide 93 94 their signatures on the consent forms before any study procedures are performed. This study 95 follows the guidelines of the Helsinki Declaration 2008, revised in 2013: Ethical Principles for Medical Research Involving Human Subjects. Subjects' rights have been protected by an 96 appropriate Institutional Review Board and written informed consent will be granted from all 97 98 subjects.

99

100 Methods

- 101
- 102 Study Design
- 103 Phase 3, randomized, double-blind, placebo-controlled trial
- 104

105 Scope of Research

Non-transfusion thalassemia patients with secondary iron overload visiting Out-patient
 department numbers 9 or 23 at the Division of Hematology, Department of Internal Medicine,
 Faculty of Medicine, Chiang Mai University, Chiang Mai, Thailand between 10th February 2025
 and 30th April 2026.

110 111

Study Population

112

113 Inclusion Criteria

- 114 Age 20-65 years
- 115 Non-transfusion dependent thalassemia [alpha or beta] diagnosis by HPLC, PCR or gene 116 mutation
- Hemochromatosis with serum ferritin 300-1000 ng/mL or > 1000 ng/mL with maximum
 iron chelator (DFP at 75 mg/kg/day or DFX at 20 mg/kg/day)
- Concurrent iron chelators without changing dose during 3 months before enrollment and
 no tendency to adjust the dose of iron chelators between study
- 121 Inform consent
- 122

123 Exclusion Criteria

- 124 Pregnancy or breastfeeding
- Chronic inflammation or other conditions that might confound serum ferritin
 interpretation
- Alanine transaminase more than 5 times upper limited of normal, creatinine clearance < 60 mL/min
- 129 Can not receive oral medication
- 130 Currently receive omeprazole or resveratrol
- 131 allergy to omeprazole or resveratrol
- 132

133 Discontinuation Criteria

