- The patients in Group 2 will take a resveratrol capsule orally twice daily (total 500 mg/day)
 in the morning and evening before meal for 6 months.
- The patients in Group 3 will take a placebo capsule orally twice daily in the morning and evening before meal for 6 months.
- All groups will receive standard treatments including iron chelators, folic acid
 supplementation, vitamin D supplementation, calcium supplementation and lifestyle
 modifications throughout the study.

Research Design

 - The patients will be appointed at the first visit, 3 months and 6 months to evaluate clinical signs, blood parameters and side-effects. If there are side effects more or equal to grade 3, the doctors may decrease the dosage of the study drug according to the following table.

	Side effects	Dose	adjustmen	t	
	Grade \geq 3 Nausea, vomiting, diarrhea, bloating	Decreased study drug 1 lev daily dose]	vel [from tw	vice daily do	ose to once
3	- In each visit, the patients will be requested to collect their blood (30 mL) which will be				hich will be
)	separated into EDTA-whole blood (5 mL) and clotted blood (25 mL). Whole blood will be				
)	used for complete blood count (CBC) analysis and Hb typing. Clotted blood will be				
	separated into the serum to be used for quantitation of kidney function biomarkers such as				kers such as
2	blood urea nitrogen (BUN) and creatinine (Cr); electrolytes (e.g., Na ⁺ , K ⁺ , Ca ²⁺ , Mg ²⁺ and			$^{2+}$, Mg ²⁺ and	
3	phosphates); liver function biomarkers such as aspartate aminotransferase (AST), alanine				
ŀ	aminotransferase (ALT) and alkaline phosphatase (ALP); and iron parameters such as				
5	serum ferritin (sFt, SI), total iron-binding capacity (TIBC), NTBI, LPI, Hcd and ERFE			l and ERFE	
6	according to the below table.				
			at at 14	and	and

Activities	1 st visit	2 nd visit	3 rd visit
History taking and physical examination			

Blood for CBC, BUN, Cr, electrolytes, AST, ALT, ALP, sFt, %TS, TIBC, SI, Hb typing, LPI, NTBI, Hcd and ERFE		
Blood for quantitation of serum vitamin B12, vitamin D, Ca^{2+} and Mg^{2+} , and determination of Hb type		
Adverse effect record		

187

188 Laboratory Investigation

- 1) CBC will be analyzed using an automated Beckman Cell Analyzer machine according to the
 manufacturer's instruction at the Central Laboratory, Maharaj Nakorn Chiang Mai Hospital,
 Faculty of Medicine, Chiang Mai University.

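### The placebo is specified as 20 mg of maltodextrin against at least 250 mg in the resveratrol capsule, with no weight matching described, so the double-blind claim rests on appearance alone

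*Protocol*

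**What the plan says.** Under Study Design the protocol describes a "Phase 3, randomized, double-blind, placebo-controlled trial". Study Intervention adds: "This study will use a double-blind technique for patients and outcome assessors". The means is that the three compounds are "filled in gelatin capsules with the same appearance as follows": "20 mg omeprazole capsule, 250 mg resveratrol capsule and 20 mg maltodextrin". On packaging it says: "The capsules will be packed in a white plastic bottle (30 capsules each) and labeled codes under the bottles".

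Every arm takes one capsule twice a day for six months. For the active arms the daily totals are given: "The patients in Group 1 will take an omeprazole capsule orally twice daily (total 40" mg/day), and "The patients in Group 2 will take a resveratrol capsule orally twice daily (total 500 mg/day"). For the third arm: "The patients in Group 3 will take a placebo capsule orally twice daily".

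The same section describes coded, opaque, sealed envelopes prepared by someone outside the study, and code lists kept from the research team. Nothing in the protocol mentions total fill weight, filler to equalise the capsules, or a check of weight.

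**The concern.** A placebo control works only if the products cannot be distinguished by those meant to be blind. The protocol promises a match in appearance and then states contents that, for placebo and resveratrol, cannot match in weight. This is a stated specification, not a detail left out: whoever prepares the placebo as written will make a capsule much lighter than the resveratrol one.

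What is at stake is the part of the trial that depends on report or judgement:

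- Adverse effects are secondary objective 4.
- The gastrointestinal complaints that can lead to a lower study-drug dose (Research Design) rest on what patients report and how it is graded, and the reduction is at the doctor's discretion.
- Some Discontinuation Criteria involve judgement, such as unsuitability to continue or a need for more chelation.
- Membership of the per-protocol set (Statistical Analysis) requires at least 80% of study drug to have been received, so adherence and stopping decide who is counted.

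Knowledge of the arm could shift any of these between resveratrol and placebo.

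**Working it through.** **Inputs, all from Study Intervention.** Omeprazole 20 mg per capsule; resveratrol 250 mg per capsule; placebo 20 mg maltodextrin; one capsule twice daily; 30 capsules per bottle.

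**1. Are these amounts per capsule?** Multiply by two capsules a day:

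- omeprazole: 20 × 2 = 40 mg/day, as stated;
- resveratrol: 250 × 2 = 500 mg/day, as stated.

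The protocol's daily totals are reproduced, so 20 mg and 250 mg are single-capsule amounts.

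**2. What do they say about total content?** For the two active capsules the figure is a drug strength; any excipient would come on top. So 250 mg is a lower bound for the resveratrol fill. The placebo has no active ingredient, and maltodextrin is the fill, so 20 mg is naturally read as its entire content.

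**3. Difference in content, resveratrol against placebo, taking the placebo at its stated 20 mg.**

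- Per capsule: 250 − 20 = 230 mg at least; ratio 250 / 20 = 12.5.
- Per bottle: 30 × 250 mg = 7.5 g against 30 × 20 mg = 0.6 g; difference 6.9 g at least.

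**4. Does the shell mask this?** Shell weight is not given. Assume 40 to 120 mg, the same for both products, and no excipient in the resveratrol capsule:

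| Assumed shell (mg) | Resveratrol capsule (mg) | Placebo capsule (mg) | Ratio | Capsules in one bottle (g) |
|---|---|---|---|---|
| 40 | 250 + 40 = 290 | 20 + 40 = 60 | 4.8 | 8.7 vs 1.8 |
| 80 | 250 + 80 = 330 | 20 + 80 = 100 | 3.3 | 9.9 vs 3.0 |
| 120 | 250 + 120 = 370 | 20 + 120 = 140 | 2.6 | 11.1 vs 4.2 |

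The shell lowers the ratio, but the absolute difference stays at 230 mg per capsule and 6.9 g per bottle. Excipient in the resveratrol capsule would widen it.

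**5. Omeprazole against placebo.** The stated figures are equal (20 mg each), but the omeprazole figure is a strength, so the text does not establish whether these two capsules match in weight.

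**The case against.** The strongest reply is that the protocol gives strengths, not fills. The placebo figure may have been written loosely to parallel the omeprazole strength, and a product specification that is not shown may provide for matched weights. This stands in part: unstated filler in the placebo cannot be excluded. But the wording as it is specifies a 20 mg placebo, and following it gives a mismatch. If the capsules are in fact matched, the text still needs correcting.

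The second reply is that the opportunity to compare is limited. Each patient takes one product and has no comparator. An uninvolved person packs the drug into coded opaque envelopes, and the code lists are withheld from the research team. This narrows the risk without removing it. The envelopes and codes hide identity and look, not weight, and the trial runs in two clinics of one hospital with 20 patients planned per arm, so supplies from several arms may pass through the same hands.

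The third reply is that serum ferritin and secondary objectives 1 to 3 are laboratory measures, and that treating doctors are not expressly named among those blinded. The point about laboratory measures stands: those outcomes are little exposed. On the doctors, the protocol is less than explicit, although keeping the code lists from the whole research team suggests that they too are meant not to know.

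A reader might go further and infer that the resveratrol arm is in effect unblinded, that capsules would rattle or show their fill level, or that the gap grows with a three-month supply. The document does not support these. It gives no shell size or opacity, a visible difference in fill would contradict the promised same appearance, and the number of bottles dispensed per visit is not stated.

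**Conclusion.** The point holds as a limited one. On the stated contents, placebo and resveratrol capsules differ by at least 230 mg each and 6.9 g per bottle, and only appearance is said to match. This assumes that the placebo holds only its stated 20 mg and that the shells are alike.

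The consequence is that someone who handles or compares both products could separate them. Whether anyone would do so is an inference, and the effect on results cannot be quantified from the document. The exposure is mainly in adverse-effect reporting, discretionary dose reduction, adherence, discontinuation and the per-protocol set. There is no basis for saying that the ferritin result is biased, or that the omeprazole and placebo comparison is affected. The change is worth making because it is cheap and protects a design feature that the protocol explicitly claims.

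**What to change.** Amend the capsule description in Study Intervention so that all three products are filled to one common total weight with inert filler, in identical opaque shells. This replaces the 20 mg maltodextrin specification for the placebo. Maltodextrin is already in use and could serve as the filler. The active contents stay as stated. Add a fill-weight check when the capsules are prepared.

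If the capsules are already matched in practice, a sentence saying so and giving the common weight is enough. If unmatched capsules have already been made, correct later batches and report the limitation alongside the adverse-effect results.

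The cost is a little more filler and a weight check. Neither the sample size nor the analysis changes.
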